1.0 OBJECTIVES

Primary Objectives

1. To determine the efficacy (response rate) of combined lirilumab and rituximab in patients with high-risk CLL as follows:
 - a. Cohort 1: refractory to and/or relapsed after at least one prior therapy OR
 - b. Cohort 2: untreated patients with high-risk molecular features such as del(17p), mutated *TP53*, del(11q), unmutated *IGHV* gene, or are >65 years of age

Secondary Objectives

1. To determine the safety of lirilumab combined with rituximab in patients with high-risk CLL.
2. To determine the progression-free survival of patients with high-risk CLL treated with lirilumab combined with rituximab.
3. To determine the overall survival of patients with high-risk CLL treated with lirilumab combined with rituximab.

Exploratory Objectives

1. To study immunological and molecular changes in the peripheral blood and bone marrow in response to lirilumab and rituximab therapy.

2.0 BACKGROUND

2.1 Chronic lymphocytic leukemia (CLL): CLL is the most common leukemia in the United States and Western hemisphere.¹ It is a disease of the aging population; the median age at diagnosis is 72 and over two-thirds of patients with CLL are over 60 years of age. Both the incidence and prevalence of this disease increase with age. The natural history for individuals with this disease is diverse. Generally, patients with early Rai stage (stage 0, low-risk) have a median expected survival of more than 10 years. Those with evidence of marrow failure manifested by anemia (stage III) or thrombocytopenia (stage IV) (Rai high-risk) have an estimated median survival of only 2 years. In patients with intermediate-risk disease (Rai stage I and II) the estimated median survival is 7 years. There is remarkable clinical diversity in patients with CLL. Following diagnosis, some patients have smoldering, asymptomatic disease that may not progress for many years; others are diagnosed with advanced stage, or early stage disease that rapidly progresses, causing symptoms and/or bone marrow failure and require treatment. Various genetic/molecular markers have been

established and validated to help in prognostication and are routinely used in clinical practice.¹ These include β 2-microglobulin, cytogenetics, immunoglobulin variable heavy chain gene (*IGHV*) mutational status, zeta chain-associated protein 70 (*ZAP-70*) expression, and CD38 expression. Presence of deletion 17p (and/or mutated *TP53*) [del(17p)] or deletion 11q [del(11q)] demonstrated by FISH as well as unmutated *IGHV* are associated with inferior clinical outcomes in patients with CLL and considered high-risk disease features.²⁻⁴ Patients with relapsed/refractory CLL constitute another group of patients with poor prognosis.^{1,5}

2.2 Immunotherapy in CLL: Immunotherapy has been an important part of CLL therapeutic armamentarium. Several strategies have been employed: a) use of monoclonal antibodies (mAb) such as anti-CD20 mAb (rituximab, ofatumumab, obinutuzumab) and anti-CD52 mAb (alemtuzumab)^{6,7}; b) use of lenalidomide⁸⁻¹⁰; c) adoptive immunotherapy with an allogeneic stem cell transplant¹¹; d) use of chimeric antigen receptor (CAR).¹² These studies highlight the fact CLL cells are amenable to immune-based therapies.

2.3 T cell dysfunction in CLL: Several studies have shown that CLL development and progression is associated with functional immune-defects in the T cell compartment.^{7,9,10,13-17} Ramsay et al. showed that T cells isolated from patients with CLL have functional defects in F-actin polymerization leading to impaired formation of immunological synapses with antigen presenting cells (APCs).⁹ Riches et al. reported that T cells from patients with CLL exhibit features of T cell exhaustion, which results in progressive loss of T cell proliferative and cytotoxicity capacity.¹⁰ Motta et al. reported increased expression of both surface and cytoplasmic cytotoxic T lymphocyte-associated antigen (CTLA-4, also known as CD152) in both CD4+ and CD8+ T cells from treatment naïve patients with CLL compared to normal donors.¹⁴ Riches et al. recently reported increased expression of programmed death-1 (PD-1, also known as CD279) receptor in T cells of patients with CLL.¹⁰ They also reported that PD-1 is preferentially expressed on CD3⁺CD8⁺CCR7⁻ effector T cells. Unlike CTLA-4 whose predominant role is at the time of T cell activation, PD-1 predominantly regulates effector T cell function in the peripheral tissues.¹⁸⁻²⁰ PD-L1 (ligand for PD-1) is also over expressed in the CLL B cells.¹³ The increased expression of CTLA-4 and PD-1 on T cells of patients with CLL and PD-L1 on the CLL cells contributes to impaired T cell function.

2.4 Natural killer (NK)-cell function in CLL: NK cells constitute 15% of peripheral blood lymphocytes and play an important role in the ability of the innate immune system to fight off viral infections and also cancer.²¹ NK cells bind to target cells through multiple receptors and binding of ligand to receptor results in activation of the NK cell, release of preformed granules containing perforin and granzymes into the target cell, and apoptosis. The activation of NK cells is regulated by a variety of activating and inhibitory receptors that are expressed by the transformed target cells. Activating receptors include NKp30, NKp44, NKp46, NKG2D, and DNAM-1. For effective activation of NK-cells tumor cells must express stress or activation ligands for activating receptors. Negative regulators of NK activating receptors include killer Ig-like receptor (KIR), CD94/NKG2A, and leukocyte Ig-like receptor-1, which recognize MHC-class 1 molecules. NK cells have the capability of binding every

cell in the body. Binding of normal cells does not result in cytotoxic activity because of the ability of NK cells to simultaneously utilize a different set of receptors to bind major histocompatibility complex (MHC) class I molecules. Binding to HLA is used as a mechanism to distinguish self from non-self, and this recognition controls the activation state of NK cells. Thus, KIR/HLA interaction directly impacts NK cell responsiveness. There are both inhibitory and activating KIR, which is one factor that results in diversity of KIR inheritance and expression. KIR is also expressed on NK cells and a small subset of T cells. Thus, mechanistically, blockade of inhibitory KIR could induce anti-tumor effects by allowing for NK cell (and possibly some T cell) activation.

Lack of KIR-HLA class I interactions have been associated with potent NK-mediated antitumor efficacy and increased survival in AML patients undergoing haploidentical stem cell transplantation from KIR-mismatched donors.²² Romagne et al. developed a monoclonal antibody that cross-reacts with KIRDL1, -2 and -3 receptors thereby blocking inhibitory signaling via these receptors. This resulted in augmented NK cell mediated lysis of tumor cells but did not induce killing of normal peripheral blood mononuclear cells, suggesting a preferential NK cell activity against AML cells.²³ Intriguingly inoculation of NK cells alone did not protect against autologous implanted AML in immunodeficient mice, however preadministration with KIR monoclonal antibody induced anti-AML activity with long-term survival.

Several studies have reported that the cytotoxic function of NK cells in patients with CLL is defective.²⁴⁻²⁷ Palmer et al. evaluated peripheral blood T cell and NK cell at diagnosis in 166 consecutive patients with newly diagnosed CLL treated at Mayo clinic.²⁷ They reported that 45% of the patients with CLL had an increase in the absolute NK cell number (upper limit of normal $0.6 \times 10^9/l$) at diagnosis. Similarly, 54% of the patients with CLL had an increase in the absolute T cell number (upper limit of normal $2.0 \times 10^9/l$) at diagnosis. This observational cohort study found wide inter-patient variation in size of the normal T cell and NK cell compartment at the time of diagnosis. It was found that smaller size of the blood T/NK cell compartments relative to the size of the circulating leukemic B-cell clone was associated with more advanced stage at diagnosis as well as unmutated *IGHV* status, raising the possibility that CLL patients with greater host immunity may experience a more indolent disease course. Both the ratio of NK:MBC (monoclonal B cell) and T:MBC correlated with time to first treatment.²⁷ Huergo-Zapico et al. evaluated NK cells in the peripheral blood at diagnosis in a group of 99 patients with CLL and 50 healthy matched controls.²⁴ Patients with CLL had significantly higher NK cell number than controls. They also reported that compared to controls, NK2GD receptor expression on NK cells was markedly decreased in patients with CLL. CD107a degranulation assay showed that NK cells of patients with CLL had diminished cytotoxic activity compared with healthy controls.²⁴

2.5 Lirilumab: Lirilumab (BMS-986015, IPH2102) is a fully human IgG4 monoclonal antibody (mAb) that is specific for a subset of human KIRs. Lirilumab is a mAb that blocks the KIR/HLA interaction, and lowers the threshold for activation of NK cells without directly activating NK cells. Lirilumab binds specifically and with high affinity to a subset of KIR,

2014-0933 Lirilumab and Rituximab for Relapsed/Refractory CLL

Version 2 – November 05, 2015

Page 3 of 27

namely KIR2DL-1, 2, and 3 and KIR2DS-1 and 2, thus preventing interaction between KIR and HLA-C. Lirilumab also is being developed in combination with the T-cell checkpoint inhibitors, ipilimumab and nivolumab. Nonclinical studies combining anti-Ly49 (5E6 F(ab')₂), the murine functional homolog of lirilumab, with the mAbs specific for the murine versions of either cytotoxic T-lymphocyte antigen 4 (CTLA-4) or programmed cell death 1 (PD-1) demonstrated enhanced anti-tumor efficacy. Lirilumab does not bind to NK cells from non-human primate or other species traditionally used for safety testing. Safety testing was performed in mice because Ly49C/I, the murine inhibitory receptors, are functionally homologous to human KIR. Mice treated with lirilumab at 10 mg/kg once weekly for 4 weeks, or the surrogate anti-Ly49 (5E6 F(ab')₂) at up to 10 mg/kg twice weekly for 13 weeks, showed no signs of toxicity.

Lirilumab is being developed for immunotherapy in patients with various hematologic malignancies and solid tumors. As of the data cut-off for this IB (29-Jul-2014), 293 subjects have been treated in 1 concluded and 3 ongoing trials: 1 monotherapy Phase 1 trial, 1 monotherapy placebo-controlled Phase 2 trial, and 2 combination therapy Phase 1 trials. Thirty-seven subjects received lirilumab monotherapy in a Phase 1 trial for patients with advanced solid tumors and hematological malignancies (IPH2102-101). One hundred fifty subjects received either lirilumab or placebo in a 2:1 ratio in a Phase 2 trial for patients with AML (IPH2102-201). IPH2102-201 is a double blind trial; thus, approximately 100 subjects received lirilumab. Eighty-eight subjects with advanced solid tumors received lirilumab in combination with nivolumab in a Phase 1 trial (CA223001). Eighteen subjects with advanced solid tumors received lirilumab in combination with ipilimumab in a Phase 1 trial (CA223002). As of 29-Jul-2014, the majority of adverse events (AEs) in these 4 ongoing trials were mild or moderate (Grade 1 or 2), self-limiting, and manageable. The most common related AEs were asthenia, fatigue, pruritus, infusion-related reaction, chills, and headache.

The first (IPH2102-101) is a monotherapy, dose escalation, Phase 1 trial to determine the maximum tolerated dose (MTD). As of the data cut-off date (July 29, 2014) a total of 37 patients have received lirilumab on this trial. Of the 20 subjects treated with lirilumab monotherapy during the dose escalation period of IPH2102-101, 3 subjects were treated with lirilumab 0.015 mg/kg, 3 subjects with 0.3 mg/kg, 4 subjects with 1 mg/kg, 4 subjects with 3 mg/kg, 3 subjects with 6 mg/kg, and 3 subjects with 10 mg/kg every 4 weeks. There were no DLTs, and the MTD was not reached. Of the 17 subjects treated with lirilumab monotherapy during the cohort expansion period of the study, 9 subjects were treated with lirilumab at 0.015 mg/kg and 8 subjects at 3 mg/kg every 4 weeks. A total of 245 AEs were reported by 36 of 37 (97%) exposed subjects. Overall, most of these AEs were mild (CTCAE Grade 1) or moderate (CTCAE Grade 2). For the 18 (48.6%) subjects who discontinued prematurely, reasons for discontinuation were disease progression (13 subjects, related AEs (3 subjects), subject's decision (1 subject), and Sponsor's decision (1 subject). AEs leading to discontinuation included urticaria, hypersensitivity, abnormal liver function test (LFT), increased gamma-glutamyl transferase (GGT), increased blood bilirubin, and papular rash, all considered to be related to study drug by the investigator.

The second (IPH2102-201) is a double-blind, placebo-controlled, Phase 2 trial of lirilumab in patients with AML who are in complete remission but ineligible for allogeneic transplant. One-third of subjects in this study will be receiving placebo. The doses of lirilumab evaluated in this maintenance AML trial were 0.1 mg/kg every 12 weeks and 1.0 mg/kg every 4 weeks. A total of 100 patients have been treated with lirilumab on this trial as of the data cut-off date (July 29, 2014). One hundred one (67%) subjects have treatment ongoing and 50 (33%) subjects discontinued prematurely. In these 50 subjects, the main (or only) reason for study discontinuation was relapse of disease (43 subjects), AEs of pancytopenia (1 subject) and acute febrile neutrophilic dermatosis (1 subject), withdrawal of consent (2 subjects), investigator decision (2 subjects), and suspicion of disease progression (2 subjects). An independent Data and Safety Monitoring Board completed safety analysis of 86 randomized subjects enrolled in this trial. On 11-Mar-2014, the members of this committee recommended continuation of the study without any modification. Adverse events were reported by 121 of 150 (81%) subjects exposed to either lirilumab or placebo. Most of these AEs were mild (Grade 1) or moderate (Grade 2). Thirty-three (22%) subjects reported Grade 3 or Grade 4 AEs (irrespective of causality) including thrombocytopenia in 5 (3%), arthralgia in 1 (<1%), neutropenia in 7 (5%), fatigue in 1 (<1%), weight increase in 2 (1%), and urinary tract infection in 1 (1%) patients. One subject reported Grade 5 pulmonary embolism, and 1 subject reported Grade 5 general physical health deterioration (corresponding to disease progression). Both of the Grade 5 events were considered by the investigator to be unrelated to study drug. Sixty-six of 150 (44%) subjects had AEs considered to be related to the study drug (either lirilumab or placebo). Most related AEs were mild or moderate in severity. Nine (6%) subjects had related Grade 3 AEs (neutropenia in 3 subjects and acute febrile neutrophilic dermatosis, sciatica, myalgia, thrombocytopenia, increased amylase, and bronchospasm in 1 subject each). One subject (0.7%) had a related Grade 4 AE of neutropenia that occurred on Cycle 1/Day 8. Adverse events evaluated as related to study drug and reported in $\geq 3\%$ of subjects were asthenia in 15 (10%) subjects, pruritus in 13 (9%) subjects, chills in 7 (5%) subjects, pyrexia in 6 (4%) subjects, and neutropenia in 5 (3%) of subjects. Five (3%) subjects reported AEs that led to study discontinuation: 4 subjects reported single events that were unrelated to study drug (lirilumab or placebo), and 1 subject reported Grade 3 acute febrile neutrophilic dermatosis that was considered related to study drug. Seventeen (11%) subjects reported SAEs during the study. The only Grade 3 or Grade 4 SAE's (irrespective of causality) seen in more than 1 subject was urinary tract infection in 2 (1%). Only 4 of 20 SAEs were considered to be related to study drug by the investigator, including one case each of Grade 4 neutropenia, Grade 3 myalgia, Grade 3 sciatica, and Grade 3 acute febrile neutrophilic dermatosis.

The third (CA223001) and fourth (CA223002) are Phase 1 trials of lirilumab in combination with either the anti-PD1 antibody nivolumab or the anti-CTLA-4 antibody ipilimumab, respectively, to determine if coordinate modulation of the innate and adaptive immune systems results in greater clinical benefit. A total of 88 subjects have received combination therapy of nivolumab and lirilumab in clinical trial CA223001 as of the data cut-off date (July

29, 2014) including 4 with lirilumab 0.1 mg/kg + nivolumab 3 mg/kg (completed), 13 with lirilumab 0.3 mg/kg + nivolumab 3 mg/kg (ongoing), 9 with lirilumab 1 mg/kg + nivolumab 3 mg/kg, and 62 with lirilumab 3 mg/kg + nivolumab 3 mg/kg. The objective of the study is to evaluate the safety of lirilumab in combination with nivolumab in subjects with advanced refractory solid tumors. Lirilumab 3mg/kg every 4 weeks in combination with nivolumab was well tolerated and was the dose administered to the majority of patients (62 of the 88 patients) on this trial (see lirilumab investigator brochure). As of the data cut-off date (29-Jul-2014), preliminary data include 18 subjects who have been treated with the combination of lirilumab and ipilimumab in clinical trial CA223002. 3 with lirilumab 0.1 mg/kg + ipilimumab 3 mg/kg (completed), 8 with lirilumab 0.3 mg/kg + ipilimumab 3 mg/kg, 6 with lirilumab 1 mg/kg + ipilimumab 3 mg/kg, and 1 with lirilumab 3 mg/kg + ipilimumab 3 mg/kg (ongoing). Two dose levels of ipilimumab (3 mg/kg and 10 mg/kg) and 4 dose levels of lirilumab (0.1, 0.3, 1, and 3 mg/kg) are being evaluated in CA223002, with 3 subjects per dose level if there is no DLT. The 5 dose cohorts are as follows (lirilumab dose + ipilimumab dose): Cohort 1: 0.1 mg/kg + 3 mg/kg; Cohort 2: 0.3 mg/kg + 3 mg/kg; Cohort 3: 1 mg/kg + 3 mg/kg; Cohort 4: 3 mg/kg + 3 mg/kg; Cohort 5: 3 mg/kg + 10 mg/kg. Subjects receive lirilumab in combination with ipilimumab every 3 weeks for a total of 4 doses (induction) and then every 12 weeks for an additional 4 doses starting at Week 24 (maintenance).

Summary of Safety: Mainly safety data are available, efficacy data available only for the IPH2102-101 and no responses observed as of the data cutoff date. As the first clinical trials with lirilumab are ongoing or recently concluded, data on safety presented herein are preliminary and subject to change. Up until 29-Jul-2014, AEs were reported by 36 of 37 (97%) subjects treated with lirilumab monotherapy (doses ranging from 0.015 mg/kg to 10 mg/kg); 121 of 150 (81%) subjects treated with blinded therapy (lirilumab or placebo [2:1]); 63 of 88 (72%) subjects treated with lirilumab 0.1, 0.3, 1, or 3 mg/kg in combination with nivolumab 3 mg/kg; and 17 of 18 (94%) subjects treated with lirilumab 0.1 mg/kg or 0.3 mg/kg in combination with ipilimumab 3 mg/kg. The majority of AEs were mild or moderate (Grades 1 or 2). To date, 12 SAEs were considered to be related to study treatment. Additional detailed safety data is available in the Lirilumab investigator brochure.

Blockade of inhibitory KIR by lirilumab is thus a promising mechanism to promote killing of tumor cells by the innate immune system. IPH2101 is the first fully-human anti-KIR monoclonal antibody, and lirilumab is the second generation. Both products bind to the same KIR subtypes with similar affinities. Functionally and biologically, the 2 antibodies are similar with the following exceptions: 1) IPH2101 is a non-recombinant protein that is produced by a murine hybridoma cell line; whereas, lirilumab is a recombinant product produced in CHO cells. 2) Lirilumab has a single amino acid substitution of a serine to a proline in the IgG4 heavy chain, resulting in greater stability of the compound by reducing the formation of half antibodies. IPH2101 studies were done prior to lirilumab studies and safety, efficacy, PKs, and immunologic correlates of IPH2101 in a phase 1 trial in elderly AML in first remission have been published (Vey N, et al., Blood, 2012 Nov 22;120(22):4317-23).²⁸ Patients received escalating doses (0.0003-3 mg/kg) of IPH2101 following a 3 + 3 design. The doses that elicited full occupancy were: 1 week = 0.075 mg/kg,

2 weeks = 1 mg/kg, and for at least 4 weeks = 3 mg/kg. There was a clear correlation between mAb exposure and KIR occupancy. The maximum tolerated dose was not reached, although full KIR saturation (> 90%) was sustained for 4 weeks only at the 3 mg/kg. Lirilumab dose of 3 mg/kg every 4 weeks is also the highest dose to be tested in BMS study of lirilumab in combination with elotuzumab for multiple myeloma: A Phase I Open Label Dose Escalation and Randomized Cohort Expansion Study of the Safety and Tolerability of Elotuzumab (BMS-901608) Administered in Combination With Either Lirilumab (BMS-986015) or Urelumab (BMS-663513) in Subjects With Multiple Myeloma” (study identifier: NCT02252263). Based on this data and the tolerability of lirilumab in combination with other agent (namely nivolumab) in the CA223001 trial we would like to evaluate lirilumab at the dose of 3.0 mg/kg every 4 weeks in this study.

For details of lirilumab preclinical studies, clinical studies, toxicities, pharmacokinetics, and adverse events please see the Lirilumab Investigator Brochure.

2.6 Rituximab: Rituxan (rituximab) is a genetically engineered chimeric murine/human monoclonal IgG1 kappa antibody directed against the CD20 antigen and is used in the treatment of B-NHL and CLL.¹

2.7 Rationale for Combined Lirilumab and Rituximab

Kohrt et al recently reported the activity of lirilumab in a KIR2DL3 transgenic lymphoma model and of anti-Ly49C/I F(ab')₂ in a C57BL/6 syngeneic lymphoma model.²⁹ In both the models tested, combination of lirilumab with an anti-CD20 monoclonal antibody significantly improved the antitumor efficacy than anti-CD20 monoclonal antibody alone. They reported that anti-Ly49C/I F(ab')₂ increased anti-CD20 mAb-mediated NK-cell degranulation and cytotoxicity and potentiated the antilymphoma activity of anti-CD20 mAb *in vivo*. They also reported that NK cells are required for the antilymphoma activity of the combination treatment. NK-cell depletion, and not macrophage, CD4, or CD8 T-cell depletion, abrogated the therapeutic efficacy of anti-CD20 mAb and anti-Ly49C/I F(ab')₂ combination therapy. These findings provide rationale for a clinical trial in B cell malignancies investigating this novel combination of an anti-KIR mAb to tilt the balance of inhibitory and stimulatory NK signals favoring spontaneous cytotoxicity and to further enhance the efficacy of rituximab by the augmentation of ADCC.

We hypothesize that enhanced CLL cell killing and improved clinical responses will be mediated by rituximab by the addition of the anti-KIR monoclonal antibody (lirilumab). The rationale for combining anti-KIR antibody and rituximab include 1) Rituximab induces both NK cell activation (via Fc-FcR engagement). Addition of anti-KIR antibody further enhances NK-cell mediated ADCC. The use of rituximab and anti-KIR antibody has been shown to be synergistic *in vitro* and *in vivo*. 2) Tumor debulking with CD20 monoclonal antibody may synergize or augment the activity of anti-KIR monoclonal antibody 3) Lirilumab and rituximab have non-overlapping and complimentary mechanisms of action and thus may synergize, with no notable increased risk for toxicity. We plan to include patients with relapsed or refractory CLL. In addition, untreated patients with high-risk cytogenetic features such as

del(17p), mutated *TP53*, del(11q), unmutated *IGHV*, or are >65 years will be eligible as they have poor outcomes and short progression-free survival with chemoimmunotherapy.

3.0 STUDY POPULATION

3.1 Inclusion Criteria

1. Patients will have a diagnosis of CLL or SLL who meet one or more criteria for active disease as defined by the International Working Group for CLL (IWCLL) and are:
 - a. Cohort 1: refractory to and/or relapsed after at least one prior therapy OR
 - b. Cohort 2: untreated patients with high-risk molecular features such as del(17p), mutated *TP53*, del(11q), unmutated *IGHV* gene, or are >65 years of age
2. Age 18 years or older
3. Eastern Cooperative Oncology Group (ECOG) Performance Status ≤ 2
4. Patients must have adequate renal and hepatic function
 - Serum bilirubin ≤ 1.5 x upper limit of normal (ULN). For patients with Gilbert's disease, serum bilirubin up to ≤ 3 x ULN is allowed provided normal direct bilirubin.
 - Serum creatinine ≤ 1.5 x ULN
 - ALT and AST ≤ 3 x ULN
5. Females of childbearing potential must have a negative serum or urine beta human chorionic gonadotrophin (β -hCG) pregnancy test result within 24 hours prior to the first dose of treatment and must agree to use an effective contraception method during the study and for 12 months following the last dose of the study drugs. Females of non-childbearing potential are those who are postmenopausal greater than 1 year or who have had a bilateral tubal ligation or hysterectomy. Males who have partners of childbearing potential must agree to use an effective contraceptive method during the study and for 31 weeks following the last dose of study drugs.
6. Patients or their legally authorized representative must provide written informed consent.

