6.0 DOSE DELAYS AND MODIFICATIONS

Patients who experience Grade 3 or 4 toxicity that can be clearly attributed to either lirilumab or to rituximab may continue treatment with the other agent while the causative agent is delayed until resolution of toxicity to grade ≤ 1 or baseline. In cases where Grade 3 or 4 toxicity cannot be attributed to a specific study drug, both study drugs should be held regardless of attribution of toxicity until the toxicity is resolved to grade ≤ 1 or baseline.

Rituximab and lirilumab administration should be delayed and increased monitoring of patients should ensue if any of the following drug-related adverse event(s) occurs:

- Any Grade ≥ 2 ALT, AST, or total bilirubin
- Any Grade ≥ 2 non laboratory non-skin drug related adverse event except for fatigue
- Any Grade ≥ 2 endocrine drug-related adverse event
- Any Grade ≥ 3 skin drug related adverse event
- Any Grade ≥ 3 drug-related laboratory abnormality (except lymphopenia or any electrolyte abnormality without any clinical sequelae that is either spontaneously reversible or resolves with clinical management to grade 2 or less within 72 hours)
- Any AE, laboratory abnormality or inter-current illness, which in the judgment of the investigator, warrants delaying the dose of study medication

Discontinuation of lirilumab will occur in the following situations:

- AST, ALT, or T Bili \geq Grade 3
- Grade 2 AST or ALT and symptomatic liver inflammation (e.g., right upper quadrant tenderness, jaundice)
- AST or ALT $> 3 \times$ ULN and concurrent total bilirubin $> 2 \times$ ULN in the absence of evidence of cholestasis (Hy's law)

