8.0 PRETREATMENT EVALUATIONS

1. Pretreatment evaluation will include a complete history and physical examination including vital signs ECOG performance status, height and weight and recording of concurrent medications (within 7 days of the first dose)
2. Complete blood count (hemoglobin, white blood cell count, platelet count, white blood count differential) (within 7 days of the first dose)
3. Clinical laboratory evaluation will include serum sodium, potassium, calcium, BUN, creatinine, glucose, phosphorous, magnesium, albumin, total protein, alkaline phosphatase, total bilirubin, ALT, AST, uric acid, LDH, β -2 microglobulin, serum immunoglobulins, lipase, amylase (within 7 days of the first dose)
4. B, T, NK cell counts and subset analyses on the peripheral blood (within 7 days of the first dose)
5. PT, aPTT (within 7 days of the first dose)
6. Urinalysis (within 7 days of the first dose)
7. HIV Ab, Hepatitis C ab, HBsAg, anti-HBcAb (within 30 days of the first dose)
8. TSH, Free T4 (within 30 days of the first dose)
9. Women of childbearing potential must have a negative serum or urine β -hCG pregnancy test result within 24 hours prior to the first dose of study drugs.
10. 12-lead EKG (within 30 days of the first dose)
11. Bone marrow aspiration and biopsy (within 60 days of the first dose if no intervening treatment for CLL given)
12. CT scan of the neck (if indicated), chest, abdomen, and pelvis with IV and oral contrast, within 30 days of the first dose. Patients with palpable cervical lymphadenopathy noted at screening physical examinations should have imaging of the neck included in their screening imaging studies and at subsequent time points for response assessment. Note: PET scan may be used instead of the CT scan imaging.

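### Inclusion 4 admits Gilbert's patients with bilirubin up to 3 x ULN, but the Section 6.0 Hy's law rule counts total bilirubin above 2 x ULN with no baseline or Gilbert's qualifier, so for some eligible patients a transaminase rise alone completes it

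*Combined protocol and SAP*

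**What the plan says.** **Entry (Section 3.1, item 4; repeated under Eligibility in the abstract).** The ordinary bilirubin limit is 1.5 x ULN. For Gilbert's disease it is wider: "For patients with Gilbert's disease, serum bilirubin up to ≤ 3 x ULN is allowed provided normal direct bilirubin". The transaminase limit has no exception: "ALT and AST ≤ 3 x ULN".

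**Discontinuation (Section 6.0; repeated in the abstract under the same title).** The list opens with mandatory wording: "Discontinuation of lirilumab will occur in the following situations". It has three items:

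1. Grade 3 or higher on any one of "AST, ALT, or T Bili".
2. Grade 2 AST or ALT with symptomatic liver inflammation.
3. AST or ALT above 3 x ULN with concurrent total bilirubin above 2 x ULN, "in the absence of evidence of cholestasis (Hy's law").

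None of the three mentions baseline, Gilbert's disease, direct bilirubin or relation to study drug. Elsewhere in Section 6.0, relation to drug qualifies the dose-delay list, and baseline appears only as a recovery target for held Grade 3 or 4 toxicity.

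**Tests (Sections 8.0 and 9.0).** The pretreatment chemistry panel in Section 8.0, item 3, includes "alkaline phosphatase, total bilirubin, ALT, AST, uric acid, LDH". The on-study panels in Section 9.0 likewise name total bilirubin. Neither section names direct bilirubin.

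**The concern.** The two sections treat the same laboratory value differently. Section 3.1 accepts a raised total bilirubin as benign when it comes from Gilbert's disease and direct bilirubin is normal. Section 6.0 counts the same value towards a mandatory stop.

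A two-part liver rule is meant to need two abnormal findings together. For a patient admitted above 2 x ULN, one of the two is present from the start, so the rule works as a transaminase rule alone. An investigator who follows the text would stop the investigational drug partly because of a value that the protocol had already accepted. An investigator who reads in a baseline allowance would depart from the text. Two patients with the same results could then be handled differently.

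A secondary gap is that the exception depends on direct bilirubin, which the test lists do not name. The listed tests therefore cannot document the condition at entry, or later help to tell Gilbert's bilirubin from a new liver event.

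**Working it through.** The plan states no figure to reproduce, so the check sets the limits side by side. Let b be total bilirubin and t the higher of ALT and AST, both in multiples of ULN.

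| Quantity | Entry limit (3.1, item 4) | Hy's law rule (6.0) | Overlap at entry |
|---|---|---|---|
| b, without Gilbert's | b ≤ 1.5 | b > 2 | none; b must rise by more than 2 − 1.5 = 0.5 |
| b, Gilbert's | b ≤ 3 | b > 2 | 2 < b ≤ 3 |
| t, all patients | t ≤ 3 | t > 3 | none; the limits meet at 3 |

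**Step 1, bilirubin half.** A Gilbert's patient at b = 2.5 is eligible, since 2.5 ≤ 3, and already meets the bilirubin condition, since 2.5 > 2. The same holds anywhere in the interval from 2 to 3. A patient admitted under the ordinary limit cannot be in this position.

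**Step 2, complete rule.** It also needs t > 3, and eligibility requires t ≤ 3. No values that satisfy inclusion 4 satisfy the whole rule.

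**Step 3, cholestasis exception.** It is unlikely to help, because the allowance itself requires normal direct bilirubin. This is an inference; the documents do not say how cholestasis is to be judged.

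**Step 4, what completes the rule later.** With b held at 2.5, a change in t from any eligible value to above 3 is enough. The first discontinuation item already stops lirilumab at Grade 3 AST or ALT whatever the bilirubin, so the conflict adds stops only while t is above 3 x ULN and still below Grade 3. The documents do not give that Grade 3 cut-off.

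**Step 5, bilirubin alone.** The first item also stops lirilumab at Grade 3 bilirubin. Section 14.0 names CTCAE v4.0, but the documents give no multiple of ULN. Suppose Grade 3 starts above g x ULN:

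- g = 3 (the assumption used here): entry and stopping limits touch without overlapping. The rise needed is anything over 3 − b, which is 0.9 from b = 2.1, 0.5 from b = 2.5 and 0.1 from b = 2.9.
- g < 3: patients with g < b ≤ 3 would meet this item outright at entry.
- g > 3: a gap of g − 3 separates the two limits.

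Steps 1 to 4 do not depend on g.

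**The case against.** **No eligible patient has to stop at entry.** A reader might infer that a Gilbert's patient must come off lirilumab on Day 1. The documents do not support that. The Hy's law rule needs a transaminase above the entry cap, and the bilirubin-only rule is not met at entry unless Grade 3 begins below 3 x ULN, which the documents do not say. This objection stands and limits the point to half of one rule.

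**The strictness may be intended.** Section 2.5 reports that, in the phase 1 monotherapy trial, related events leading to discontinuation included abnormal liver function tests and raised bilirubin. A sponsor could reasonably want no exception. That is possible, but Section 6.0 does not say so, and silence beside an express allowance in Section 3.1 leaves the investigator to guess.

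**The hepatic rule is not weakened.** A reader might infer that a liver signal would be missed. The error runs the other way: without an exception the rule fires more readily. The cost is possible over-stopping.

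**Response and toxicity results need not be distorted.** The rule stops lirilumab only. Under Section 12.0, patients who stop for reasons other than progression stay on study with disease assessments, so they can still be counted as responders. Toxicity in Section 14.0 requires at least a possible relation to treatment. Section 11.1 has the investigator assign attribution and has baseline conditions recorded with their grade. Effects on the response rate or on a toxicity look are therefore speculative and form no part of this point.

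**Section 8.0 is not a full list of eligibility tests.** It does not itemise FISH, *TP53* or *IGHV* testing either, and the separate schedule-of-evaluations file named in the abstract is not reproduced. Section 3.1 already makes normal direct bilirubin a condition of entry. This is fair, and it makes the direct-bilirubin gap secondary. Listing the test is still useful, since this eligibility condition rests on it.

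**Conclusion.** The point holds in a limited form. For eligible Gilbert's patients with total bilirubin above 2 and up to 3 x ULN, the two-part Hy's law rule in Section 6.0 works as a transaminase-only rule, because its bilirubin half is met before treatment for a reason that Section 3.1 accepts. This follows from the documents' own limits and needs no outside figure.

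The bilirubin-only rule adds to the problem only under an assumption. If Grade 3 starts above 3 x ULN, it abuts the entry limit and a small rise from near that limit would trigger it.

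The likely consequence is unnecessary stopping of lirilumab in a subset of at most 48 patients. The documents do not say how many will have Gilbert's disease, so the effect cannot be sized; it is probably small. Sample size, the response and toxicity boundaries and their operating characteristics are unaffected. It is more than missing detail, because following the text forces a stop that rests partly on an accepted entry value.

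**What to change.** Reconcile inclusion 4 with the Section 6.0 discontinuation list, and make the same change in the abstract's eligibility and dose-modification text. Section 6.0 should state how each of its total-bilirubin limits is read for a patient admitted under the Gilbert's allowance. If no exception is intended, it should say that. Which rule applies is for the sponsor's clinical team, and none is proposed here.

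For these patients, list direct bilirubin in Section 8.0, item 3, and in the Section 9.0 chemistry panels, because Section 3.1 makes eligibility depend on it.

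The cost is amendment wording in Sections 3.1, 6.0, 8.0 and 9.0 and the abstract, plus one further analyte for a few patients, run on the chemistry sample already drawn. No statistical section needs to change.
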